5.2.1.2 Dose Modification and Toxicity Management Guidelines for Pembrolizumab

Dose modification and toxicity management for immune-related AEs associated with pembrolizumab

Adverse events associated with pembrolizumab exposure may represent an immunologic etiology. These irAEs may occur shortly after the first dose or several months after the last dose of pembrolizumab treatment and may affect more than one body system simultaneously. Therefore, early recognition and initiation of treatment is critical to reduce complications. Based on existing clinical trial data, most irAEs were reversible and could be managed with

interruptions of pembrolizumab, administration of corticosteroids and/or other supportive care. For suspected irAEs, ensure adequate evaluation to confirm etiology or exclude other causes. Additional procedures or tests such as bronchoscopy, endoscopy, skin biopsy may be included as part of the evaluation. Based on the severity of irAEs, withhold or permanently discontinue pembrolizumab and administer corticosteroids. Dose modification and toxicity management guidelines for irAEs associated with pembrolizumab are provided in [Table 3](#); additional guidance is provided Section 5.6.1.

For subjects whose dose was withheld due to toxicity, subjects may resume pembrolizumab upon resolution of toxicity to Grade 0-1 or baseline. This dose would be considered Day 1 of the next cycle and should be in alignment with the new schedule.

Table 3 Dose Modification and Toxicity Management Guidelines for Immune-related AEs Associated with Pembrolizumab

General instructions:				

 1. Corticosteroid taper should be initiated upon AE improving to Grade 1 or less and continue to taper over at least 4 weeks. 2. For situations where pembrolizumab has been withheld, pembrolizumab can be resumed after AE has been reduced to Grade 1 or 0 and corticosteroid has been tapered. Pembrolizumab should be permanently discontinued if AE does not resolve within 12 weeks of last dose or corticosteroids cannot be reduced to ≤ 10 mg prednisone or equivalent per day within 12 weeks. 3. For severe and life-threatening irAEs, IV corticosteroid should be initiated first followed by oral steroid. Other immunosuppressive treatment should be initiated if irAEs cannot be controlled by corticosteroids. 				

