	Grade 4 or recurrent Grade 3	Permanently discontinue		

a. For subjects with liver metastasis who begin treatment with Grade 2 AST or ALT, if AST or ALT increases by greater than or equal to 50% relative to baseline and lasts for at least 1 week then subjects should be discontinued.
 
b. Withhold or permanently discontinue pembrolizumab is at the discretion of the investigator or treating physician.
 
NOTE: For subjects with Grade 3 or 4 immune-related endocrinopathy where withhold of pembrolizumab is required, pembrolizumab may be resumed when AE resolves to \leq Grade 2 and is controlled with hormonal replacement therapy or achieved metabolic control (in case of T1DM).
				

Dose modification and toxicity management of infusion-reactions related to pembrolizumab

Pembrolizumab may cause severe or life threatening infusion-reactions including severe hypersensitivity or anaphylaxis. Signs and symptoms usually develop during or shortly after drug infusion and generally resolve completely within 24 hours of completion of infusion. Dose modification and toxicity management guidelines on pembrolizumab associated infusion reaction are provided in Section 5.6.1 (Table 5).

Other allowed dose interruption for pembrolizumab

Pembrolizumab may be interrupted for situations other than treatment-related AEs such as medical / surgical events or logistical reasons not related to trial therapy (e.g., elective surgery, unrelated medical events, subject vacation, and/or holidays). Subjects should be placed back on trial therapy within 12 weeks of the scheduled interruption, unless otherwise discussed with the Sponsor. The reason for interruption should be documented in the subject's trial record.

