7.2.3.2 Events of Clinical Interest

Selected non-serious and serious adverse events are also known as Events of Clinical Interest (ECI) and must be recorded as such on the Adverse Event case report forms/worksheets and reported within 24 hours to the Sponsor either by electronic media or paper. Sponsor Contact information can be found in the Investigator Trial File Binder (or equivalent).

Events of clinical interest for this trial include:

1. an overdose of Sponsor's product, as defined in Section 7.2.1 - Definition of an Overdose for This Protocol and Reporting of Overdose to the Sponsor, that is not associated with clinical symptoms or abnormal laboratory results.
2. an elevated AST or ALT lab value that is greater than or equal to 3X the upper limit of normal and an elevated total bilirubin lab value that is greater than or equal to 2X the upper limit of normal and, at the same time, an alkaline phosphatase lab value that is less than 2X the upper limit of normal, as determined by way of protocol-specified laboratory testing or unscheduled laboratory testing.*

*Note: These criteria are based upon available regulatory guidance documents. The purpose of the criteria is to specify a threshold of abnormal hepatic tests that may require an additional evaluation for an underlying etiology. The trial site guidance for assessment and follow up of these criteria can be found in the Investigator Trial File Binder (or equivalent).

3. Additional adverse events:

irAEs as defined in Section 5.2.1.2.

ECIs (both non-serious and serious adverse events) from the date of first dose through 90 days following cessation of treatment, or 30 days after the initiation of a new anticancer therapy, whichever is earlier, need to be reported to the Sponsor **within 24 hours** of the event, regardless of attribution to study treatment, consistent with standard SAE reporting guidelines and either by electronic media or paper. Sponsor Contact information can be found in the administrative binder.

Subjects should be assessed for possible ECIs prior to each dose. Lab results should be evaluated and subjects should be asked for signs and symptoms suggestive of an immune-related event. Subjects who develop an ECI thought to be immune-related should have additional testing to rule out other etiologic causes. If lab results or

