	Likely Cause	Is the AE not reasonably explained by another etiology such as underlying disease, other drug(s)/vaccine(s), or other host or environmental factors

Relationship to Sponsor's Product (continued)	The following components are to be used to assess the relationship between the test drug and the AE: (continued)	
	Dechallenge	Was the Sponsor's product discontinued or dose/exposure/frequency reduced? If yes, did the AE resolve or improve? If yes, this is a positive dechallenge. If no, this is a negative dechallenge. (Note: This criterion is not applicable if: (1) the AE resulted in death or permanent disability; (2) the AE resolved/improved despite continuation of the Sponsor's product; or (3) the trial is a single-dose drug trial; or (4) Sponsor's product(s) is/are only used one time.)
	Rechallenge	Was the subject re-exposed to the Sponsor's product in this study? If yes, did the AE recur or worsen? If yes, this is a positive rechallenge. If no, this is a negative rechallenge. (Note: This criterion is not applicable if: (1) the initial AE resulted in death or permanent disability, or (2) the trial is a single-dose drug trial); or (3) Sponsor's product(s) is/are used only one time). NOTE: IF A RECHALLENGE IS PLANNED FOR AN ADVERSE EVENT WHICH WAS SERIOUS AND WHICH MAY HAVE BEEN CAUSED BY THE SPONSOR'S PRODUCT, OR IF REEXPOSURE TO THE SPONSOR'S PRODUCT POSES ADDITIONAL POTENTIAL SIGNIFICANT RISK TO THE SUBJECT, THEN THE RECHALLENGE MUST BE APPROVED IN ADVANCE BY THE SPONSOR CLINICAL DIRECTOR AS PER DOSE MODIFICATION GUIDELINES IN THE PROTOCOL.
	Consistency with Trial Treatment Profile	Is the clinical/pathological presentation of the AE consistent with previous knowledge regarding the Sponsor's product or drug class pharmacology or toxicology?
The assessment of relationship will be reported on the case report forms /worksheets by an investigator who is a qualified physician according to his/her best clinical judgment, including consideration of the above elements.		
Record one of the following	Use the following scale of criteria as guidance (not all criteria must be present to be indicative of a Sponsor's product relationship).	
Yes, there is a reasonable possibility of Sponsor's product relationship.	There is evidence of exposure to the Sponsor's product. The temporal sequence of the AE onset relative to the administration of the Sponsor's product is reasonable. The AE is more likely explained by the Sponsor's product than by another cause.	

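### Table 3 withholds pembrolizumab for myocarditis at Grade 1 or 2, but the general resume rules allow re-dosing at Grade 1 and no myocarditis resume criterion is written

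*Combined protocol and SAP*

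**What the plan says.** All the dosing rules at issue are in Section 5.2.1.2.

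- **Myocarditis row of Table 3:** withhold at Grade 1 or 2; permanently discontinue at Grade 3 or 4. Corticosteroids are given according to severity. The row states no condition for resuming.
- **Text before Table 3**, for any dose withheld for toxicity: "subjects may resume pembrolizumab upon resolution of toxicity to Grade 0-1 or baseline".
- **Table 3, general instruction 1:** "Corticosteroid taper should be initiated upon AE improving to Grade 1 or less and continue to taper over at least 4 weeks".
- **Table 3, general instruction 2:** "pembrolizumab can be resumed after AE has been reduced to Grade 1 or 0 and corticosteroid has been tapered". It continues: "Pembrolizumab should be permanently discontinued if AE does not resolve within 12 weeks of last dose". Failure to bring steroids down to the stated dose within 12 weeks is the other ground for stopping.
- **NOTE under Table 3:** a separate resume grade for one group, beginning "For subjects with Grade 3 or 4 immune-related endocrinopathy where withhold of pembrolizumab is required". These subjects may resume at Grade 2 or lower once the condition is controlled.

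Two provisions elsewhere bear on re-dosing. Section 7.2.3.2 lists "irAEs as defined in Section 5.2.1.2" among the events of clinical interest, and requires 24-hour reporting of "ECIs (both non-serious and serious adverse events) from the date of first dose through 90 days following cessation of treatment", with an earlier cut-off if new anticancer therapy starts. Table 9 in Section 7.2.4 says that, where an event was serious and possibly drug-caused, or where re-exposure poses additional significant risk, "THE RECHALLENGE MUST BE APPROVED IN ADVANCE BY THE SPONSOR CLINICAL DIRECTOR AS PER DOSE MODIFICATION GUIDELINES IN THE PROTOCOL".

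**The concern.** A Grade 0-1 resume rule works without difficulty where withholding starts at Grade 2 or above: the subject has to leave the withheld grades before the drug restarts. The myocarditis row withholds from Grade 1, so Grade 0 is the only grade at which it does not bar dosing. Both general resume rules nevertheless reach Grade 1, and nothing exempts myocarditis from them.

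This is a matter of patient safety. A site following the written rules can re-expose a subject to the drug at a grade of cardiac toxicity for which the same table orders it withheld. The site must work out for itself which instruction governs, for a toxicity whose Grade 3-4 form ends treatment.

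**Working it through.** No arithmetic applies and the plan gives no figure to reproduce. The check sets the rules side by side.

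**1. Grades.** Myocarditis withhold grades: {1, 2}. Discontinue grades: {3, 4}. General resume grades, in the text and in instruction 2: {0, 1}. Withhold and resume grades share {1}.

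**2. Following each onset grade through the rules.**

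| Onset | Text before Table 3 | Instruction 2 | Row at Grade 1 |
|---|---|---|---|
| Grade 2, improves to Grade 1 | Resume grade met | Resume grade met; any steroid must also have been tapered | Withhold |
| Grade 1, unchanged | Met if read literally; not met if *resolution* requires improvement | Not met: *reduced to* implies a fall, hence Grade 0 | Withhold |

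For the Grade 2 onset, both rules permit dosing at Grade 1. For the Grade 1 onset there are two readings:

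- Read literally and alone, the text is satisfied on the day the event starts, so the Grade 1 hold has no effect under it.
- If improvement is required, which is also the result of applying the text and instruction 2 together, the Grade 1 onset must reach Grade 0. The Grade 2 onset needs only Grade 1, so the more severe event has the looser threshold.

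Neither outcome looks intended in a row that withholds from the lowest grade.

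**3. Search for an exception.** Footnote a concerns AST/ALT in subjects with liver metastases. Footnote b gives discretion for Grade 3-4 hypophysitis and hyperthyroidism. The NOTE covers Grade 3-4 endocrinopathy. Sections 5.2.2, 5.6.1, 5.8.1 and 7.1.1.9 contain no resume criterion for myocarditis.

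**4. Does the 12-week rule impose Grade 0?** It depends on the event failing to *resolve*. The text before Table 3 treats Grade 0-1 or baseline as resolution, and Section 7.1.5.3.1 follows adverse events until resolution to Grade 0-1. On that usage, myocarditis persisting at Grade 1 counts as resolved, and the rule does not require Grade 0.

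**5. Do the safeguards settle the grade?** The 24-hour report is notification, not approval. The Table 9 requirement is an approval gate where it applies. A non-serious Grade 1 or 2 case need not meet its first condition, and the second, additional significant risk, is a judgement. The gate sets no grade and refers back to the dose modification guidelines, where the gap lies.

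**The case against.** The strongest reply is that a grade that triggers a hold and a grade that permits resumption are different things, and Table 3 treats them so elsewhere. Hypophysitis is withheld at Grade 2, yet the NOTE lets a Grade 3-4 case resume at controlled Grade 2. AST/ALT is withheld at Grade 2, yet a subject who entered at Grade 2 may resume at baseline, which is Grade 2. This part stands. A reader might infer that myocarditis is the only row where withhold and resume grades overlap, and the documents do not support that. But the hypophysitis overlap comes from a written exception with a control condition, and the AST/ALT overlap from the subject's own starting value. For myocarditis the overlap comes only from general rules, and the reply does not remove the reversed thresholds for Grade 1 and Grade 2 onsets.

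A reader might also infer that the text before Table 3, having no taper condition, lets a steroid-treated subject restart weeks earlier than instruction 2 would. That is not supported either. Instruction 2 covers every situation in which the drug was withheld, the text sends the reader to Table 3, and the two read naturally as cumulative. Section 5.5.2 also prohibits giving study drug with corticosteroids above physiologic doses.

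It is also fair to say that the resume wording is permissive, that the row asks for evaluation of etiology, that subjects are assessed for events of clinical interest before each dose, and that Table 9 can require advance Sponsor approval. A reader who inferred that the plan directs re-dosing, or leaves it unchecked, would go too far. None of these provisions tells the site which grade permits resumption.

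One could answer that the specific row overrides the general rules. But the row states no resume criterion and the documents state no order of precedence.

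**Conclusion.** The gap is real, and it should be closed at the next amendment. The written rules permit re-dosing at Grade 1 myocarditis after a Grade 2 event, although the row withholds at Grade 1. For a Grade 1 onset they either leave the hold without effect or set a stricter threshold than for Grade 2. The Grade 2 result follows from the current text on either reading; the Grade 1 result depends on whether *resolution* requires improvement.

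The size cannot be given as a number of subjects, because the documents give no myocarditis frequency. Nothing here bears on response rate, power or the type I error rate. That Grade 0 is the right threshold is a proposal based on the row's own hold at Grade 1; the documents do not establish it. The sponsor could choose another criterion, but should state one.

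**What to change.** Add a footnote to the myocarditis row of Table 3: *Resume only after resolution to Grade 0 with any corticosteroid tapered; the general Grade 0-1 resume rules do not apply. For myocarditis, 'resolve' in the 12-week rule means Grade 0.* Add to the resume sentence before Table 3: *except myocarditis, see Table 3.*

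The second sentence of the footnote is needed. Without it, a subject with persistent Grade 1 myocarditis could not be dosed, yet would count as resolved under the 12-week rule and so would not be discontinued by it.

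The cost is one footnote and one cross-reference at the next amendment, plus a notice to sites. No procedures or subjects are added. The downside is that any subject whose myocarditis persists at Grade 1 stays off drug and is discontinued at 12 weeks. The hold is what the row already directs; the discontinuation is new.

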5.2.2 Timing of Dose Administration

Study drug should be administered on Day 1 of each cycle after all procedures/assessments have been completed as detailed on the Trial Flow Chart (Section 6.0). Study drug may be administered up to 3 days before or after the scheduled Day 1 of each cycle due to administrative reasons.

All study drug will be administered on an outpatient basis.

Pembrolizumab will be administered as a 30 minute IV infusion every 2 weeks (treatment cycle intervals may be withheld due to toxicity as described in Section 5.2.1.2). Sites should make every effort to target infusion timing to be as close to 30 minutes as possible. However, given the variability of infusion pumps from site to site, a window of -5 minutes and +10 minutes is permitted (i.e., infusion time is 30 minutes: -5 min/+10 min).

The Pharmacy Manual contains specific instructions for pembrolizumab dose calculation, preparation of the infusion solution, and administration.

Continuing Study Drug Administration After Initial Evidence of Radiologic Disease Progression

Immunotherapeutic agents such as pembrolizumab may produce antitumor effects by potentiating endogenous cancer-specific immune responses. The response patterns seen with such an approach may extend beyond the typical time course of responses seen with cytotoxic agents, and can manifest as a clinical response after an initial increase in tumor burden or even the appearance of new lesions.

If initial radiologic imaging shows PD, tumor assessment should be repeated ≥ 4 weeks later in order to confirm PD with the option of continuing treatment per below while awaiting

radiologic confirmation of progression. If repeat imaging shows a reduction in the tumor burden compared to the initial scan demonstrating PD, treatment may be continued as per treatment calendar. If repeat imaging confirms progressive disease, subjects will be discontinued from study therapy (exception noted in Section 7.1.2.5.1). In determining whether or not the tumor burden has increased or decreased, Investigators should consider all target lesions as well as non-target lesions (please refer to the Procedures Manual).

When feasible, subjects should not be discontinued until progression is confirmed; however, the decision to continue study treatment after the 1st evidence of disease progression is at the Investigator’s discretion based on the clinical status of the subject as described in [Table 4](#) below. Subjects may receive study treatment while waiting for confirmation of PD if they are clinically stable as defined by the following criteria:

- Absence of signs and symptoms (including worsening of laboratory values) indicating disease progression
- No decline in ECOG performance status
- Absence of rapid progression of disease
- Absence of progressive tumor at critical anatomical sites (e.g., cord compression) requiring urgent alternative medical intervention

Table 4 Imaging and Treatment After First Radiologic Evidence of Progressive Disease

	Clinically Stable		Clinically Unstable	
	Imaging	Treatment	Imaging	Treatment
1 st radiologic evidence of PD	Repeat imaging at ≥ 4 weeks to confirm PD	May continue study treatment at the Investigator’s discretion while awaiting confirmatory scan	Repeat imaging at ≥ 4 weeks to confirm PD if possible	Discontinue treatment
Repeat scan confirms PD	No additional imaging required	Discontinue treatment (exception noted in Section 7.1.2.5.1)	No additional imaging required	N/A
Repeat scan shows SD, PR or CR	Continue regularly scheduled imaging assessments every 8 weeks (after 6 months, imaging assessments every 12 weeks)	Continue study treatment at the Investigator’s discretion	Continue regularly scheduled imaging assessments every 8 weeks (after 6 months, imaging assessments every 12 weeks)	May restart study treatment if condition has improved and/or clinically stable per Investigator’s discretion

CR=completed response; N/A=not applicable; SD=stable disease; PD=progressive disease; PR=partial response

5.2.3 Trial Blinding/Masking

This is an open-label trial; therefore, the Sponsor, investigator and subject will know the treatment administered.

5.3 Randomization or Treatment Allocation

Subjects participating in this trial will be allocated by non-random assignment.

5.4 Stratification

No stratification based on age, sex or other characteristics will be used in this trial.

5.5 Concomitant Medications/Vaccinations (Allowed & Prohibited)

Medications or vaccinations specifically prohibited in the exclusion criteria are not allowed during the ongoing trial. If there is a clinical indication for any medication or vaccination specifically prohibited during the trial, discontinuation from trial therapy or vaccination may be required. The investigator should discuss any questions regarding this with the Sponsor Clinical Director. The final decision on any supportive therapy or vaccination rests with the investigator and/or the subject's primary physician. However, the decision to continue the subject on trial therapy or vaccination schedule requires the mutual agreement of the investigator, the Sponsor and the subject.

5.5.1 Acceptable Concomitant Medications

All treatments that the investigator considers necessary for a subject's welfare may be administered at the discretion of the investigator in keeping with the community standards of medical care. All concomitant medication will be recorded on the electronic case report form eCRF including all prescription, over-the-counter (OTC), herbal supplements, and IV medications and fluids. If changes occur during the trial period, documentation of drug dosage, frequency, route, and date may also be included on the eCRF.

All concomitant medications received within 28 days before the first dose of trial treatment and 30 days after the last dose of trial treatment should be recorded. Concomitant medications administered after 30 days after the last dose of trial treatment should be recorded for SAEs and ECIs as defined in Section 7.2.

5.5.2 Prohibited Concomitant Medications

Subjects are prohibited from receiving the following therapies during the Screening and Treatment Phase (including retreatment for post-complete response relapse) of this trial:

- Anti-cancer systemic chemotherapy or biological therapy

Note: Subjects with glioblastoma multiforme with any prior bevacizumab treatment are not eligible (exceptions may be considered after consultation with the sponsor).

Note: Subjects with prostate cancer who are currently on LHRH analogs and subjects with breast cancer receiving LHRH analogs for ovarian suppression to avoid menses are eligible for this study and may continue to take the LHRH analogs while participating in this study.

- Immunotherapy not specified in this protocol
- Chemotherapy not specified in this protocol
- Investigational agents other than pembrolizumab
- Radiation therapy

Note: Radiation therapy to a symptomatic solitary lesion or to the brain may be allowed after consultation with Sponsor.

- Live vaccines within 30 days prior to the first dose of trial treatment and while participating in the trial. Examples of live vaccines include, but are not limited to, the following: measles, mumps, rubella, chicken pox, yellow fever, rabies, BCG, and typhoid (oral) vaccine. Seasonal influenza vaccines for injection are generally killed virus vaccines and are allowed; however intranasal influenza vaccines (e.g. Flu-Mist®) are live attenuated vaccines, and are not allowed
- Glucocorticoids for any purpose other than to modulate symptoms from an adverse event.

Note: The use of physiologic doses (e.g., prednisone 10 mg) of corticosteroids may be approved after consultation with the Sponsor. Concomitant administration of higher steroid doses with study medication is prohibited.

Note: Systemic steroid therapy allowed for subjects in the GBM cohort as long as \leq dexamethasone 4 mg, or its steroid equivalent (other exceptions may be considered after sponsor consultation).

Note: Use of prophylactic corticosteroids to avoid allergic reactions (e.g. IV contrast dye) is permitted.

Subjects who, in the assessment by the investigator, require the use of any of the aforementioned treatments for clinical management should be removed from the trial. Subjects may receive other medications that the investigator deems to be medically necessary.

The Exclusion Criteria describes other medications which are prohibited in this trial.

There are no prohibited therapies during the Post-Treatment Follow-up Phase.

